# **11.1 HLQ – Missing Data Guidelines**

Guidelines for missing responses in the HLQ questionnaire include: Overall rule

- if >50% data is missing, then do not add it up or include it in further analysis.
- If exactly or less than 50% is missing then average the available responses for that scale and include in analysis.

Scales with 4 items/questions (i.e. scales 1 and 2)

- If missing data in 3 or more items, this scale should be excluded for this participant (i.e. leave cells blank for all items in that scale)
- If missing data in 1 or 2 items, scale can be included.

Scales with 5 items (scales 3, 4, 5, 6, 8, 9)

- If missing data in 3 or more items, this scale should be excluded for this participant (i.e. leave cells blank for all items in that scale).
- If missing data in 1 or 2 items, scale can be included.

Scales with 6 items (scale 7 only)

- If missing 4 or more answers should also be excluded as above.
- If missing 3 or less items, scale can be included.

# **12** Sensitivity Analyses

To account for COVID-19 effects of the UK lockdown (on Monday 23rd March 202) during part of the study, a patient-level binary factor for this will be created by using the date of the 12-month assessment relative to this. As both co-primary endpoints of "emotion" and "handicap" (i.e. participation) may be affected by this event, a sensitivity analysis will be conducted by repeating the primary analyses but now including this new variable.

As a sensitivity analysis, the co-primary end-points will also be analysed under the assumption that missing data is either "missing completely at random" or "missing at random". In this instance, multiple imputation will be used to impute missing outcome data and the various potential predictors of missingness will be included in the imputation model.

Multiple imputation for cluster randomised trials should be based on a multilevel imputation model (Karla Diaz-Ordaz, 2014). For example, missing data will be imputed under different assumptions such as X=4 or X=5 and the primary analysis repeated to check the impact of this. Altering X to be different values: 5,6,7,8. Will eventually mean a "significant" result disappears and that might happen at say 7, which is the tipping point.

# **13** Safety Analyses

Patient-level safety data collected during the trial will be included in the reporting of safety events, from the point of patient consent to participate in the trial until the end of the follow-up period or loss to follow-up.

Coding of safety events (e.g. MedDRA) is not being utilised in the IPCAS trial.

# 13.1 Adverse Events

An adverse event (AE) is defined as any untoward medical occurrence in a patient or clinical investigation subject who has been administered any research procedure. The trial team will not formally record or report non-serious AEs. No statistical analysis will be performed on non-serious AEs.

# **13.2** Serious Adverse Events

A serious adverse event (SAE) is defined as any adverse event or effect that results in death; is life threatening; requires hospitalisation or prolongation of existing hospitalisation; results in persistent or significant disability/incapacity; is a congenital anomaly/birth defect; or is an otherwise medically important event. The trial team will formally record and report all SAEs.

The statistical analysis of SAE data will include a simple summary table of SAEs with one row per SAE. The number of SAEs in the trial is expected to be low given the nature of the intervention, and given that no formal coding system is being used for safety events the data will not be further categorised to provide a summary based on frequency of SAE types.

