# 4.2 Purpose of the analyses

These analyses will assess the efficacy and safety of a novel model of primary care for stroke survivors living in the community compared to standard care. A health economic analysis plan (HEAP) will be documented separately.

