#### 8.2.3 Safety Population

The safety population comprises all consented patients, regardless of whether they received any study intervention, including control, and regardless of length of time in the study. The safety population will be used to provide summary statistics on adverse events.

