# 9 Summary of Study Data

Summary data will be provided for a variety of study data via tables and/or graphs as outlined in *IPCAS SAP V1.0\_23April2020 figures and tables listing.xlsx*.

Where results are presented as summary statistics, continuous variables will be summarised using the following descriptive statistics:

- n (the non-missing sample size)
- mean
- standard deviation
- median
- 25th percentile
- 75th percentile
- maximum
- minimum.

Where results are presented as summary statistics, categorical variables will be summarised using frequency and percentages (based on the non-missing sample size) of all observed levels. Non-observed levels should also be included if they form part of an expected set of category levels (e.g. from a categorical questionnaire question with a finite set of response options).

In general, summary statistics will be presented in tables by treatment and by gender, with a column for each treatment group or gender. If appropriate, a table may also be split by questionnaire number (baseline, 3 months, 6 months, etc). For study data that is summarised in a more raw form and without the need for summary statistics (e.g. recruitment, withdrawals, SAEs, etc), data will be presented in a table or graph as appropriate. The quantity of missing data will also be summarised for relevant outcomes, by treatment group, at 6months at also 12 months.

Descriptive statistics for Intervention fidelity will be presented as detailed in Section 6 (*IPCAS V1.0\_23April2020 figures and tables.docx.*)

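### The SAP's stated aim of comparing safety with standard care is met in its text only by a one-row-per-SAE table, and the documents do not say how the 14 categories in protocol Section 17 enter the SAE dataset

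*SAP*

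**What the plan says.** **Purpose and population.** SAP 4.2 states that the analyses will assess the "safety of a novel model of primary care for stroke survivors living in the community compared to standard care". SAP 8.2.3 defines the safety population as all consented patients, controls included, and adds: "The safety population will be used to provide summary statistics on adverse events".

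**Output.** SAP Section 9 has a general default that summary statistics are tabulated by treatment and by gender. The same paragraph then sets some data apart: "For study data that is summarised in a more raw form and without the need for summary statistics (e.g. recruitment, withdrawals, SAEs, etc"). For those data it promises a table or graph, whichever is suitable. SAP 13.1 states: "The trial team will not formally record or report non-serious AEs". SAP 13.2 names one product: "The statistical analysis of SAE data will include a simple summary table of SAEs with one row per SAE". It also declines a summary by frequency of SAE type, because no coding system is used. SAP Section 19 lists a group of safety and SAE outputs, whose shells are in a separate file.

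**Which events count.** SAP 13.2 defines an SAE as an adverse event or effect that, among other criteria, "results in death; is life threatening; requires hospitalisation or prolongation of existing hospitalisation". It continues: "The trial team will formally record and report all SAEs". It also says: "The number of SAEs in the trial is expected to be low given the nature of the intervention". Protocol Section 17 asks each principal investigator to tell the chief investigator within 24 hours of SAEs that are not on a list of 14 categories. It makes the chief investigator responsible for seeing that all SAEs are assessed for expectedness and relatedness, and for passing the non-exempt ones to the sponsor.

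**The concern.** There are two separate gaps.

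The first is the form of the output. A comparison with standard care needs, at the least, the number of patients with an event and the number at risk in each arm. A table with one row per event gives neither. If arm is not a column, it does not even give a count of events by arm. If arm is a column, the reader must still work out which rows belong to the same patient and find the denominators elsewhere.

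The second is the content of the table. The SAP describes its SAE data as complete and does not mention the list in the protocol. A reader of the final report could not tell from these documents whether a table headed as all SAEs includes cardiovascular deaths, recurrent strokes and cardiovascular admissions. In a trial of stroke survivors those are events a reader would look for.

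**Working it through.** No figure in the plan has to be reproduced here. The check is a comparison of passages and a count.

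**1. Does the SAP text commit to a by-arm safety summary?**

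| Place | What it implies for SAEs |
|---|---|
| SAP 4.2 | A comparison with standard care is intended |
| SAP 8.2.3 | Summary statistics on adverse events will be produced |
| SAP 9, general default | Summary statistics are split by treatment |
| SAP 9, later in the same paragraph | SAEs are an example of data that need no summary statistics |
| SAP 13.1 | Non-serious events are neither recorded nor analysed |
| SAP 13.2 | One named output, with one row per SAE |

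Under SAP 13.1, the only adverse events left for SAP 8.2.3 to summarise are SAEs. SAP Section 9 treats SAEs as not needing summary statistics. The two statements cannot both be followed, and SAP 13.2 does not say which prevails. Sections 8.2.3 and 9 together give some basis for a by-arm summary, but the section written for SAEs commits only to the listing.

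**2. How many categories does protocol Section 17 list, and do they overlap with the SAP definition?**

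- Bullets in the list: 14.
- Elective or pre-planned surgery: 1. Cardiovascular or thromboembolic: 14 − 1 = 13.
- Bullets that name death or hospitalisation in their own words: 5 (cardiovascular death; heart failure with admission; unstable angina with admission; any cardiovascular admission; admission for elective or pre-planned surgery).
- Of these, cardiovascular: 5 − 1 = 4. These four meet the SAP 13.2 definition on its face. The elective-surgery item may not count as untoward.
- The PCI item is stated to include non-serious events.

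The list and the SAP definition therefore overlap, and the definition is not limited to events caused by the intervention. The SAP's expectation of few SAEs rests on the nature of the intervention, so it cannot be judged until it is known whether listed events count.

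**3. Is there a route for listed events into the SAE dataset?**

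- Protocol 17: the reporting duty on principal investigators excludes listed events. The duty to assess covers all SAEs, but no route to the chief investigator is given for the listed ones. The sponsor's records cover what the trial team reports to it.
- Protocol 15.2.1: mentions SAE information passing between the team and practices, with no detail of which events.
- Protocol 15.2: defers details to a data management plan that is not available here.
- SAP Table 1: schedules SAE monitoring throughout, without naming a source.
- Protocol 9.2 (review of general practice notes) and SAP 9.1 (death as a withdrawal reason): either could pick up some listed events, but neither is linked to SAE reporting.

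No available passage gives the route, and none says that listed events are left out.

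**The case against.** The other side has a fair case.

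- *The by-arm default applies.* SAP Section 9 tabulates summary statistics by treatment as a rule, and SAP 8.2.3 promises such statistics on a population that includes controls. This stands in part: there is some textual basis for arm-level summaries. It does not settle the matter, because the same paragraph of Section 9 singles out SAEs as not needing them.
- *The listing is not exclusive.* SAP 13.2 says the analysis will include it, and the shells may show arm. Both are true. A reader might infer that no by-arm SAE table is planned, but the documents do not support that, since the shells cannot be seen. Nor does the absence of a table number in SAP Section 13 support it. The dose models in SAP 10.2.1 and the sensitivity analyses in SAP Section 12 cite none either.
- *The protocol list is an exemption from expedited reporting.* Section 17 separates assessment of all SAEs from onward notification of the non-exempt ones, which fits that reading well. A reader might infer that cardiovascular deaths and recurrent strokes will be missing from the SAE table. The documents do not show this. What remains is that the route is not stated.
- *Part of the remedy exists.* Withdrawals, with death among the reasons, have their own summary tables, and the CONSORT diagram can supply denominators. The oversight committee considers the safety profile. This helps, but none of it gives patients with at least one SAE by arm.
- *With few events and no coding, a listing is reasonable.* Accepted as regards event types. A count of patients by arm needs no coding.

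**Conclusion.** The point holds as a minor one, worth a cheap improvement. The SAP passages on safety output conflict, and the listing that SAP 13.2 names does not by itself deliver the comparison announced in SAP 4.2. The SAP and protocol Section 17 also need to be reconciled on which events make up the SAE data.

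For size, 14 categories are in question, 4 of which are cardiovascular and meet the SAP definition on their face. The documents give no event rates, so the number of events cannot be estimated. The SAE table may be incomplete, but this is not shown.

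The conclusion rests on the available text alone. The table shells could already answer the first gap, and the data management plan the second. No efficacy inference is affected.

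**What to change.** (a) Reconcile protocol Section 17 with SAP 13.2 on which events enter the SAE dataset and by what route, and head the SAE table to match: all SAEs, or SAEs outside the listed categories. Which events should be exempt is not judged here.

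(b) Add to SAP 13.2 one descriptive table by arm on the safety population, with denominators: number of SAEs, patients with at least one SAE, and deaths. It needs no test and no coding, and the decision not to summarise by event type can stay. Adjust SAP Section 9 so that it no longer conflicts. If the shells already contain this table, citing its number in SAP 13.2 is enough.

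The cost is a few sentences, a cross-reference and one small table from SAE data already planned. The downside is that counts may be low, so the table can only be descriptive.

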# 14 Health Economic Analyses

A health economic analysis plan (HEAP) will be prepared separately by the trial health economist. The HEAP will document the planned health economic analyses.

# **15 Reporting Conventions**

P-values ≥0.001 will be reported to 3 decimal places; p-values less than 0.001 will be reported as "<0.001". The majority of summary statistics will be reported to one decimal place greater than the original data. Exceptions include minimum and maximum which will use the same number of decimal places as the original data. Exceptions may be made where appropriate. Estimated parameters, not on the same scale as raw observations (e.g. regression coefficients) will be reported to 3 significant figures.

# **16 Technical Details**

At the time of writing, the statistical documents for the IPCAS trial are stored on the "Projects" network drive at the MRC Biostatistics Unit, within a main folder named "IPCAS". Study documents, including the SAP and protocol, are stored within the sub-folder: \IPCAS\Documents.

Current and previous statistical analyses for IPCAS (including data, statistical code, and output) are stored within the sub-folder: \IPCAS\Analysis.

At the time of writing, it is anticipated that the statistical analyses will be performed in R Studio or Stata. The results will be assembled into an XML report, where each page of output should also contain a title and figure/table number, as well as a page number, author, date and time, and the file path and name of the code file that produced the output.

# **17** Summary of Changes to the Protocol

This statistical analysis plan does not proposes any changes to the statistical approach described in the protocol (*Trial Protocol v1.1\_28-02-2018.pdf*). Supplemental analysis of fidelity not outlined in the protocol is described in Section 10.2.1 above.

# **19** Listing of Tables and Figures

Listing of tables and figures are in file:

• IPCAS SAP V1.0\_23April2020 figures and tables listing.xlsx.

Skeleton figures and tables are in file:

• IPCAS SAP V1.0\_23April2020\_figures and tables.docx.

Figures and tables are listed under the following sections:

- 1. Trial recruitment
- 2. Trial Progression
- 3. Baseline demographics
- 4. Withdrawals
- 5. Descriptive statistics Scores
- 6. Descriptive statistics Fidelity
- 7. Analysis Primary outcome
- 8. Analysis Secondary outcomes
- 9. Analysis Intervention subgroup and Fidelity
- 10. Analysis Safety and SAEs
